4. TRIAL SCHEDULE

Table 3. Study Timeline

Task	Year 1				Year 2			
	1	2	3	4	1	2	3	4
Obtain IRB approval								
Register study with www.clinicaltrials.gov								
Subject screening and recruitment (n=60, ~2-6/month)								
Baseline assessments								
Neurogenic Bladder Symptom Score (NBSS) (SA 1.2)								
Incontinence quality of life (I-QOL) (SA 2.1)								
Anticholinergic Side Effects (SA 2.2)								
Collection of Voiding Diary Weekly								
Overactive Bladder Medication dosage (SA 1.1)								
Cath frequency, volumes, and incontinence (SA 1.2)								
Compliance								
Evaluate the efficacy of TTNS at home (SA 1)								
Evaluate the impact of TTNS on quality of life (SA 2)								
Analyze SA 1 & SA 2								
Present findings								
Development of manuscript(s)								

5. STUDY DESIGN

Anticipated number of patients to screen: 80

- Anticipated number of patients to enroll: 60
- Anticipated drop out or loss to follow-up: 6

Approximate time to complete study recruitment: 1 year

Expected duration of subject participation: 3-months. 3-months was selected as a fair assessment of efficacy. Clinically, medications are determined efficacious based on 1-month or less of use.

TTNS protocol: Same TTNS setting will be used as protocols HSC-MS-15-0806 and HSC-MS-17-0423. Electrodes 2 inch by 2 inch will be placed according to anatomic landmarks, with the negative electrode behind the internal malleolus and the positive electrode 10cm superior to the negative electrode, verified with rhythmic flexion of the toes secondary to stimulation of the flexor digitorum and hallucus brevis. The intensity level will be set to the amperage immediately under the threshold for motor contraction. If there is not contraction seen, patients will be excluded. In addition, if the patient perceives pain, the intensity will be lowered until comfortable. Stimulation frequency of 10 Hz and pulse width of 200ms in continuous mode will be used.^{13, 14}

Sham protocol and rationale: Toe flexion will be attempted, as in the TTNS protocol. Then the stimulation will be reduced to 1 mA for 30 minutes. Rationale: In order to make this a convincing blind, the TTNS protocol must be simulated closely as subjects may interact and discuss. Rather than turning the device off, they will be instructed that the stimulation required is below motor threshold, at 1 mA. Based on the knowledge of the pilot trial requiring about 40mA for TTNS, and the amperage for needle-driven PTNS adjacent to the tibial nerve at 0.5 – 1mA, it is unrealistic that 1mA via surface electrodes is sufficient to activate the tibial nerve. Both TTNS and sham participants will be instructed to use the device for 30 minutes, 5 days per week.

Medication reduction protocol: Subjects will be using up to 2 anticholinergic OAB medications. Subjects generally use similar medications with a common approach- maximize one medication before adding a second medication. The PI will provide a weekly weaning schedule, individualized for each subject. No changes will occur during the first 2 weeks of TTNS. Starting week 3, the secondary OAB medication will be halved if possible, otherwise discontinued. Should the subject tolerate this, weaning will continue until one medication is discontinued, then the other. If the subject does not tolerate weaning, they will remain on the lowest, tolerable dose and we will attempt weaning the following week.

- Information gathered:
 - Clinical demographics, morbidity, and Neurologic Exam findings from interview with subjects, exam, and EMR review.
 - Bladder diary will include:
 - use of TTNS with amperage and presence of toe flexion, and pain score 0-10
 - log of catheterization, volumes
 - log of incontinence episodes
 - Description of other observed changes, including but not limited to: fatigue, vision changes, mental status, bowel program changes, and sexual function changes.
 - I-QOL at baseline initial visit and then at 3-month follow-up. Can be conducted over phone.

- NBSS at baseline and every 4 weeks (monthly) and at the 3-month follow-up. Can be conducted over phone.
- Anticholinergic survey at baseline and then at 3-month follow-up. Can be conducted over phone.
- TTNS satisfaction survey at 3-month follow-up. Can be conducted over the phone.
- Information will be tabulated on an Excel spreadsheet on my personal work desktop, password protected. Any paper data (bladder diary) will be de-identified and retained in a locked drawer in the locked office of the PI.
- General self-efficacy at baseline, week 6 and at the end of the trial. Can be conducted over the phone.
- CD-RISC at baseline, week 6 and at the end of the trial. Can be conducted over the phone.
- The medication and TTNS adherence survey at baseline then every 4 weeks. Can be conducted over the phone.
- The medication and TTNS % survey at baseline then every 4 weeks. Can be conducted over the phone.

1. Summary of Study Design

A randomized control trial of TTNS v sham-control in chronic SCI (n=60) performing intermittent catheterization on OAB medications will be performed to address the following Specific Aims:

In Specific Aim 1, we will assess the efficacy of TTNS based on reduced OAB medication use over 3 months while maintaining stable NGB symptoms based on NBSS score. A bladder diary will also capture important information such as frequency and volume of catheterization, incontinence episodes, and other related observations.

In Specific Aim 2, we will assess whether TTNS improves incontinence-related QOL based on I-QOL survey scores.

Schedule of events Home RCT													
Procedures	Baseline	Week 1	Week 2	Week 3	Week 4	Week 5	Week 6	Week 7	Week 8	Week 9	Week 10	Week 11	End of Study/ week 12
Review study procedures; Informed consent & privacy	x												
Eligibility criteria for study entry	x												
Demographics	x												x
Medical / SCI history	x												
Urodynamic study	x												x
IQOL	x												x*
NBSS	x				x*				x*				x*
Anticholinergic Suvery	x												x*
Voiding diary data	x*	x*	x*	x*	x*	x*	x*	x*	x*	x*	x*	x*	x*
TTNS Survey Satisfaction													x*
AE reporting and follow up	x*	x*	x*	x*	x*	x*	x*	x*	x*	x*	x*	x*	x*
Qualitative Experience													
Medication Adherence	x				x				x				x
TTNS Adherence					x				x				x
Medication %	x				x			x					x
TTNS %					x			x					x
CD-RISC	x					x							x
Self-efficacy	x					x							x

* Will be completed over the phone

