- Potential for progressive SCI including neurodegenerative SCI, ALS, cancer myelopathy, Multiple sclerosis, transverse myelitis
- History of central nervous system disorder (i.e. prior SCI, stroke, brain injury, Parkinson's disease, MS, etc.)
- History of peripheral neuropathy
- pre-SCI symptoms of peripheral neuropathy (numbness and/or tingling in feet, sharp/jabbing/burning pain in feet, sensitivity to touch, lack of coordination, muscle weakness, etc.)
- Pregnancy
- Known injury to the lumbosacral spinal cord or plexus, or pelvis with associated neuropathy
- concern for tibial nerve pathway injury
- absence of toe flexion or autonomic dysreflexia during electric stimulation test
- bladder chemodenervation in prior 6 months

5. Withdrawal Criteria

Possible reasons for discontinuation of study intervention:

- Intolerable incontinence after discontinuation of bladder medications
- Intolerant to electric stimulation
- Non-compliance

To mitigate non-compliance, a stipend for effort in completing voiding diary will be provided at \$10 per day (2 days per month). An additional \$20 will be provided for logging bladder medication use and TTNS use/settings monthly. If both voiding diary and TTNS diary are reported, a \$10 bonus will be provided, therefore \$70 month 1, and \$50 for each months 2 and 3. At most per subject= \$170 for the 3-month trial per subject. Subjects will also receive reimbursement for travel for the urodynamic studies up to \$200 per trip (two urodynamic studies = up to \$400 per subject) and if medication reduction requires new prescriptions to cover co-payments when applicable up to \$50 total per subject.

6. Subject Replacement

Subjects who drop out will be replaced by recruitment from the SCI clinic and asking for informed consent from those who meet the I/E criteria.

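### Logged device amperage nearly identifies the arm and sits in records open to the PI, who is meant to be blinded and sets each medication wean

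*Combined protocol and SAP*

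**What the plan says.** **Settings.** Section 5 (Study Design) says of TTNS: "The intensity level will be set to the amperage immediately under the threshold for motor contraction". It cites about 40 mA from the pilot. Sham is fixed at 1 mA for everyone, and "they will be instructed that the stimulation required is below motor threshold, at 1 mA". The stated reason for a careful sham is that "the TTNS protocol must be simulated closely as subjects may interact and discuss".

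**Recording.** Under the information gathered in Section 5, the bladder diary includes "use of TTNS with amperage and presence of toe flexion, and pain score 0-10". Section 6, item c, repeats that amperage and toe flexion go in the bladder diary. Section 3.5 pays participants "for logging bladder medication use and TTNS use/settings monthly". None of these exempts the sham arm.

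**Who holds the records.** Section 5: "Any paper data (bladder diary) will be de-identified and retained in a locked drawer in the locked office of the PI"; and "Information will be tabulated on an Excel spreadsheet on my personal work desktop, password protected". Section 10.2 describes a shared-drive spreadsheet that receives voiding-diary and survey data, with access controlled by the PI. Section 10.1 has the PI review anomalies, and Section 14 has the PI retain source documents.

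**Blinding and its safeguards.** Section 6.2 blinds the PI and gives allocation to the RA. Diaries are de-identified, data carry a subject ID, and the RA keeps the linking log (Sections 10.2 and 12.3).

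**The PI's part in the endpoint.** Section 5: "The PI will provide a weekly weaning schedule, individualized for each subject". The same paragraph sets rules: no change for two weeks; from week 3, halve or stop the secondary drug; go on if this is tolerated; if not, stay at the lowest dose that is tolerated and try again a week later.

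**The concern.** The main issue is the PI. The variable that best separates the arms is stored with data that the PI holds, controls and queries, and the same PI decides week by week how far each participant is weaned. Medication reduction is the endpoint on which the sample size rests (Section 11.1, Aim 1.1). A PI who came to know the arm could, without intending it, push harder in one arm or accept a report of intolerance sooner in the other. Either would look like a TTNS effect, and blinding lost during the trial cannot be restored at analysis.

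The secondary issue is the participant. The plan foresees that participants may talk, yet gives sham participants a specific number that differs sharply from what TTNS participants will read on their devices. Tolerance of the wean, the NBSS, the voiding diary and the I-QOL all depend on the participant, so a sham participant who worked out the arm might stop weaning earlier or report worse symptoms.

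**Working it through.** **How informative is the setting?** 40 mA / 1 mA = 40-fold, using Section 5's figures. TTNS settings vary by person and are lowered for pain, so 40 is a typical value only. Sham is always 1 mA, so a single logged entry nearly identifies the arm of that record. Toe flexion and pain score, logged alongside, are weaker cues of the same kind.

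**Can the PI reach it?** Setting the sections side by side:

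- Section 5 and Section 6 item c put amperage in the bladder diary, and Section 5 puts the paper diary in the PI's office.
- Section 10.2 sends voiding-diary data to a spreadsheet whose access the PI controls; Section 10.1 has the PI resolve anomalies.
- Section 3.5 mentions a TTNS diary as distinct from the voiding diary, and Section 6.4 mentions a TTNS log. A separate record may therefore exist already. No section says that it is kept away from the PI.

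**Can the PI link a coded record to a person?** Not through the linking log. Indirectly, perhaps: the PI writes each weaning schedule, and Table 3 appears to collect medication dose with the weekly voiding diary. At the 2 to 6 recruits a month in Table 3 and three months each, about 2 × 3 = 6 to 6 × 3 = 18 participants would be in follow-up at once, ignoring dropout. A dose pattern that the PI prescribed could be recognisable in a group of that size.

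**What could such bias do? Illustration only.** Assume no true effect and 40% reducing medication in each arm (Section 11.1's control rate). Let an assumed share f of sham reducers fail to reduce because of unblinding, with the TTNS rate unchanged. Then:

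- sham rate = 0.40 × (1 − f)
- apparent difference = 0.40 × f
- sham reducers lost = 0.40 × n × f

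Take n = 21 (Section 11.1's requirement), 30 (recruited) and 27 = (60 − 6)/2 (Section 5's six dropouts). Section 11.2 names no test for proportions, so both the pooled z-test and Fisher's exact test are shown. Probabilities of a two-sided 0.05 result favouring TTNS, by exact binomial enumeration:

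| f | Sham rate | Difference | Reducers lost (n = 21 / 30) | Pooled z (n = 21 / 27 / 30) | Fisher (n = 21 / 27 / 30) |
|---|---|---|---|---|---|
| 0 | 0.40 | 0 points | 0 / 0 | 0.0251 / 0.0233 / 0.0244 | 0.0102 / 0.0124 / 0.0129 |
| 0.10 | 0.36 | 4 points | 0.84 / 1.2 | 0.0463 / 0.0470 / 0.0486 | 0.0201 / 0.0267 / 0.0278 |
| 0.25 | 0.30 | 10 points | 2.1 / 3.0 | 0.1050 / 0.1177 / 0.1205 | 0.0513 / 0.0724 / 0.0770 |
| 0.50 | 0.20 | 20 points | 4.2 / 6.0 | 0.3103 / 0.3771 / 0.3924 | 0.1909 / 0.2632 / 0.2978 |

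The plan states no figure of its own for this bias, so there is none to reproduce.

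**The case against.** The best defence has four parts.

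*The PI path has a missing link.* Amperage shows the arm of a subject ID, not of a person. The RA holds the key and captures diary data by weekly phone call. Section 14 is about retention, Section 10.1 gives no timing for anomaly review, and nothing says when paper diaries reach the PI's office. This stands as a limit: a reader might infer that the PI will be unblinded, and the documents do not show that. They show only that nothing beyond coding prevents it.

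*The PI's discretion is bounded.* The weaning rules in Section 5 leave less room than the word individualized suggests. This also stands, although judging tolerance and setting the steps still leave some room.

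*A separate TTNS log may exist.* Sections 3.5 and 6.4 point that way; Section 5 and Section 6 item c point the other way. The diary form itself is not reproduced. The text is unsettled, which is a reason to settle it.

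*The participant path is speculative.* A reader might infer that the 1 mA instruction tells sham participants their arm. It does not: both arms run below motor threshold, and a sham participant who compares with nobody has a plausible account. How often participants of a home treatment would compare settings is unknown. What TTNS participants are told may be in the consent form, which is not available for review, so silence on that cannot count against the plan.

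Finally, f is an assumption that combines the share unblinded with the share who then fail to wean. Nothing in the documents supports f = 50%, and the 19–39% range in that row should not be read as the trial's false-positive rate.

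**Conclusion.** The concern holds for the PI. The plan states a blind and then leaves a near-certain marker of the arm in records that the blinded person keeps, controls and queries, while that person also steers the primary endpoint. De-identification, subject IDs and the RA-held linking log reduce the exposure but do not close it, since doses and diary content may allow recognition. It is a weaker and secondary point for participants, where it depends on how often they compare settings.

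The size of any bias is unknown. The 40-fold contrast rests on the pilot's typical setting, and the probabilities in the table rest wholly on an assumed f, so they carry no weight in judging how serious this is. The case for change is that the gap is specific and inexpensive to close before weaning decisions are exposed to it.

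**What to change.** **Main change (Section 5, information gathered; Section 6, item c; Sections 10.1 and 10.2).**

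- Record amperage, toe flexion and pain score only on the TTNS log, not in the bladder diary or the main spreadsheet.
- Keep that log and its data file with the RA, who already manages allocation and so learns nothing new.
- Have the RA or the statistician, not the PI, review its anomalies until the analysis is complete.
- Continue to report pain and skin adverse events to the PI, without the setting.

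The cost is one separate sheet and file and a reassigned check, with no extra staff. Sample size, endpoint and device are unchanged, and settings are still recorded for dose monitoring. The downside is that the PI cannot check settings during the trial. A pain report may still hint at the arm, which has to be accepted for safety.

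**Secondary change, a partial remedy (Section 5, sham protocol).** Give both arms the same truthful wording with no number, for example: 'the stimulation used is below the level that moves your toes'. Do not describe the setting as individual: that is untrue for sham, and two sham participants who compared would find it contradicted. Participants asked to log amperage must be able to read it, and no section shows that the device can hide it, so the cue is reduced but remains.

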6. METHODS AND ASSESSMENTS

- a. Physical exam will be performed per usual care at TIRR, by the attending SCI physicians. Data will be retrieved from the electronic medical record and placed into the data spreadsheet. Missing data will be requested from the attending physician or directly from the patient.
- b. Transcutaneous Tibial Nerve Stimulation (TTNS) will be placed by trained research assistants in the clinic to determine if the subject meets I/E criteria. Skin inspection will be performed before and after the trial stimulation session at the electrode sites. Blood pressure will also be monitored during this trial for an additional safety measure to ensure autonomic dysreflexia is not occurring.
- c. The Bladder diary will be used to collect data use of TTNS with amperage and presence of toe flexion, pain score 0-10, as well as incontinence episodes and volumes. The research assistant (RA) will call weekly to capture the written data and monitor progress with the protocol.
- d. The RA will also perform the survey outcome measures (NBSS, I-QOL, CD-RISC, GSE, Medication adherence surveys and anticholinergic side effect questionnaire) at baseline every 4 weeks, 6 weeks and at 3-months. Surveys can be conducted over the telephone.

2. Randomization and Blinding

Subjects will be randomized to either TTNS or sham control (1:1) using a block size of 4 and stratified based on complete/incomplete SCI to ensure the equal allocation of the most severely injured in the two groups. The PI will be blinded to randomization and treatment allocation, managed by the research assistant.

3. Contraception and Pregnancy Testing

Females of childbearing age will have to adhere to medically recommended contraception if sexually active with men, such as condoms and/or birth control pills.

4. Study Visits and Procedures

- *Screening Visits and Procedures*

Screening will be performed in the SCI clinic by the PI or co-I SCI attendings.

Those that meet the I/E criteria will be approached for the study by the PI or co-I attendings. They have until the study period is complete to decide whether they want to participate. However, they will have to return to clinic to have the TTNS trial performed and the directions for home use.

- *Study Visits and Procedures*

Subjects will have their first study visit after their normal clinic visit. Once consented, we will trial TTNS for a response of toe flexion. If they have a response, they will be included in the study. If no response or not tolerating electric stimulation, they will not be included in the study.

Participants will have direction in clinic on the use of the Stamobil+, including written, oral, and smartphone images/video if they have access.

The electric stimulation protocol will use stimulation frequency of 10 Hz and pulse width of 200ms in continuous mode for 30 minutes daily, beginning as soon as possible. The goal is 5 days per week of TTNS use for 3-months.

Subjects will be called weekly to capture the information of the TTNS log and to monitor progress of protocol. They will also be reminded to change electrodes weekly. 3 days prior to the NBSS call, the RA will contact the subjects to remind them to begin recording in their voiding diary for 2 days.

- *Final Study Visit:*

Upon completion of the 3-month study period, final voiding diary information will be collected and the post-trial questionnaires will be conducted.

- *Post Study Follow up and Procedures*

The data will be statistically analysed in the post-study follow up. Subject participation is not required.

- *Discontinuation Visit and Procedures*

If withdrawal occurs, no evaluation will be required for the final study visit, regardless of the withdrawal reason. There are no safety risks in withdrawing from this study at any point. OAB medications can be resumed at the prior efficacious dose.

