9. SAFETY MEASUREMENTS

1. Definitions

An adverse event is any unfavourable and unintended sign, symptom, or disease temporally associated with the use of a medical treatment or procedure that may or may not be considered related to the medical treatment or procedure.

The FDA definition of unanticipated adverse device effect will be used, as followed: *An unanticipated adverse device effect* as defined by FDA regulations at 2CFR 812.3(s) – Any serious adverse effect on health or safety or any life-threatening problem or death caused by, or associated with, a device, if that effect, problem, or death was not previously identified in nature, severity, or degree of incidence in the investigational plan or application (including a supplementary plan or application), or any other unanticipated serious problem associated with a device that relates to the rights, safety, or welfare of subjects.

Skin irritation, inflammation, and electrode burn beneath the electrodes are potential adverse events directly related to the use of electric stimulation.

2. Collecting, Recording and Reporting of Adverse Events

The Investigator will be responsible for collecting and reporting adverse events during the UDS. The research assistant and the PI will collect adverse events related to the randomized control trial.

Grading of the severity of the adverse events will be made by the PI, using the Common Terminology Criteria for Adverse Events v4.0 developed by the National Cancer Institute. The relevant “Burn” category is included below.

DERMATOLOGY/SKIN						Page 1 of 3
Adverse Event	Short Name	Grade				
		1	2	3	4	5
Burn	Burn	Minimal symptoms; intervention not indicated	Medical intervention; minimal debridement indicated	Moderate to major debridement or reconstruction indicated	Life-threatening consequences	Death

REMARK: Burn refers to all burns including radiation, chemical, etc.

Reporting procedures for:

- Deaths and life-threatening events
- other SAEs
- Other adverse events

The PI will report problems according to the UTHSC-Houston IRB policy, specifically in the event which in the opinion of the PI is both unexpected and related and places subjects or others at risk of harm.

The PI will report the reportable events to CPHS via iRIS within 7 days, unless the report involves the death of a participant, in which case the report needs to be provided to CPHS within 24 hours.

3. Safety Monitoring Plan

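### Weekly adverse-event calls are scheduled, but the visible text specifies no targeted skin or autonomic dysreflexia question, and no skin inspection after the clinic test, over about 60 home sessions per participant

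*Combined protocol and SAP*

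**What the plan says.** **At the clinic test.** Section 6.b provides that "Skin inspection will be performed before and after the trial stimulation session at the electrode sites" and that "Blood pressure will also be monitored during this trial for an additional safety measure to ensure autonomic dysreflexia is not occurring". I read 'this trial' as the test stimulation session, because the section 5 schedule of events has no blood pressure row. Dysreflexia during the test is an exclusion (section 3.4 and Table 2).

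**At home.** The section 5 diary records "use of TTNS with amperage and presence of toe flexion, and pain score 0-10", along with catheterization and incontinence logs. It also has an open item: "Description of other observed changes, including but not limited to: fatigue, vision changes, mental status, bowel program changes, and sexual function changes". Its examples mention neither skin nor dysreflexia.

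**Scheduled contact.** The schedule marks "AE reporting and follow up" by phone at baseline and in each of weeks 1 to 12. Section 6.4 describes the call: "Subjects will be called weekly to capture the information of the TTNS log and to monitor progress of protocol". Section 9.2 adds that "The research assistant and the PI will collect adverse events related to the randomized control trial", and it assigns events at the urodynamic studies to the investigator. None of these places says how adverse events are to be asked about.

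**Harms named.** Section 9.1 states: "Skin irritation, inflammation, and electrode burn beneath the electrodes are potential adverse events directly related to the use of electric stimulation". Section 9.2 prints a severity table for one event, burn. Section 2.4.c lists urinary tract infection, worsened incontinence, pain with stimulation and skin irritation, and describes a response when redness persists to the next day. It mentions neither burn nor dysreflexia.

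**The concern.** The plan anticipates certain stimulation harms and then, as far as the text shows, does not ask about them once stimulation moves to the home. It has a grading table for burns but no stated data item that feeds it. It has a response to next-day redness but no stated field that records next-day redness. It treats dysreflexia on stimulation as reason enough to exclude a person, yet describes no later enquiry about it.

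The prompted item, pain, is weakest where it is needed most. Randomization is stratified by complete or incomplete injury, so participants with complete injury are expected, and some may not feel the electrode site.

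The timing also matters. The dysreflexia check precedes medication weaning, which starts in week 3 (section 5), and section 1 links pathologic bladder reflexes to dysreflexia. A check at baseline says little about the weaning weeks.

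At stake is how far a low or zero count of skin or dysreflexia events can be trusted, and whether the two arms can be compared on them. Section 1 itself describes the safety of home TTNS as a gap in knowledge.

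**Working it through.** **1. Number of home sessions.** The documents state no total, so there is no plan figure to reproduce. Inputs: 5 days per week for 3 months (section 6.4) and a schedule that ends at week 12 (section 5).
- 5 x 12 = 60 per participant at full compliance.
- If 3 months is taken as 13 weeks: 5 x 13 = 65.
- Section 6.4 also says daily just before giving the 5-day goal. Read literally, that is 7 x 12 = 84. The two statements need to be reconciled; the point does not depend on which is meant.

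**2. Scheduled contact.** There are 12 weekly calls after baseline: 60 / 12 = 5 home sessions per adverse-event contact.

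**3. Named harms against stated collection.**

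| Harm | Where the plan raises it | Check at clinic test | Targeted home item stated | Open or general route at home |
|---|---|---|---|---|
| Pain | 2.4.c | Tolerance of stimulation | Yes, 0-10 score | Yes |
| Skin irritation, inflammation | 2.4.c (irritation), 9.1 | Inspection before and after | None | Yes |
| Electrode burn | 9.1, graded in 9.2 | Inspection before and after | None | Yes |
| Autonomic dysreflexia | Exclusion (3.4, Table 2), 6.b | Blood pressure | None | Yes |

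The last column is filled throughout, because weekly adverse-event contact and the open diary item exist. The gap is in the column before it.

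**4. What a zero count would mean.** Suppose no event of a given kind is recorded in n = 30 TTNS participants, all followed. The one-sided 95% upper bound p on the per-participant risk solves (1 - p)^30 = 0.05:
- Exact: p = 1 - 0.05^(1/30) = 9.5%.
- Rule of three: 3 / 30 = 10%.

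If an affected participant is recorded only with probability c, the recorded risk is c x p, so the bound becomes (1 - 0.05^(1/30)) / c, or approximately 3 / (30c).

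| Capture c (assumed) | Exact / c | Rule of three / c |
|---|---|---|
| 100% | 9.5% | 10% |
| 75% | 9.5 / 0.75 = 12.7% | 10 / 0.75 = 13.3% |
| 50% | 9.5 / 0.50 = 19.0% | 10 / 0.50 = 20% |

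The documents give no capture rate, so the lower rows only illustrate sensitivity. The direction is not in doubt: incomplete capture always raises the bound. Dropout among the 30 would raise it too.

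**The case against.** The strongest reply is that the plan has an adverse-event system and that its content cannot be judged from the visible text. Contact is weekly, responsibility is assigned, and the diary's open item is expressly not limited to its examples. The case report form and sample voiding diary, where such questions would normally sit, are listed as appendices but not reproduced. All of this stands. A reader might infer that harms at home rest on spontaneous report. The documents do not support that, since a scheduled weekly adverse-event contact is more than waiting for a participant to volunteer something. Nor can one say that the calls contain no prompt, only that none is specified in the text available. Setting the single inspected session against all home sessions as a coverage ratio would mislead for the same reason: it ignores the 12 weekly contacts.

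Second, dysreflexia is not among the device harms listed in section 9.1. It is a screening exclusion and a concern monitored at the test, and section 2 hopes that TTNS will reduce it. That is right, and the point should not call it a listed device harm. It remains an event that the plan regards as possible during stimulation.

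Third, skin irritation is already described in section 2.4.c. That also stands: what that section lacks is burn and dysreflexia.

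Fourth, this is an efficacy trial, its safety monitoring centres on urinary tract infection, and a home-safety conclusion is not a stated objective. This limits the severity. It does not remove the value of a usable record of harms by arm.

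**Conclusion.** The point holds in a limited form. Weekly adverse-event contact and an open diary item exist, but the visible text specifies no targeted question on electrode-site skin or dysreflexia and no skin inspection after the clinic test, over about 60 home sessions per participant at full compliance. The one prompted tolerability item, pain, may miss skin injury in participants with reduced sensation.

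Two features add some weight. Intolerance to stimulation is a reason for withdrawal (section 3.5), yet withdrawal requires no final evaluation (section 6.4), so a harm that ends participation may go uncharacterized. And allocation is managed by the research assistant (section 6.2), the same role that makes the weekly calls; unscripted questioning by someone who may know the arm leaves room for unequal recording.

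On size, a zero count in 30 would exclude a risk above about 10% if capture were complete, and only above about 13% or 19-20% at assumed capture of 75% or 50%. A reader might take 20% as a property of this plan; it is not, because it follows from an assumed capture rate. The verdict also assumes that the unseen appendices do not already contain the missing items. It is a low-cost improvement in data capture, not a flaw that threatens the efficacy analysis.

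**What to change.** Add two fixed yes/no items to the home log and to the existing weekly adverse-event call, worded identically in both arms:
1. Electrode-site skin: redness still present the next day, blister or burn.
2. Symptoms of autonomic dysreflexia during or after a session.

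Add burn and dysreflexia to the safety endpoints in section 2.4.c, beside the skin irritation already described there, and report all of them by arm. Both arms wear electrodes, so the sham arm helps to separate reactions to the adhesive from effects of the current.

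If the case report form or sample diary already has these items, no new item is needed; align the protocol text with them.

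The cost is two log items and a line in the script of calls already being made. The downside is that more minor skin events will be recorded. This is data capture only and proposes no change to stimulation, medication or care.
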